5.1.1. Screening Period

This is a screening period of not less than 3 days and not more than 42 days. In exceptional circumstances, the screening window can be extended after consultation with the Sponsor. Patients will be screened for study eligibility at Visit 1 and will be randomized at Visit 2 to continue in Part A.

5.1.2. Parts A and B: 24-Week Double-Blind Placebo-Controlled (Part A) Period and 28-Week Open-Label (Part B) Period

Patients on a background of MTX will be randomized at a 1:1 ratio to 1 of 2 treatment arms (baricitinib or placebo):

- Patients randomized to baricitinib will be administered a 4-mg tablet QD (or 2 mg baricitinib tablet QD if eGFR <60 mL/min/1.73 m²) starting at Week 0 (Visit 2) through Week 52 (Visit 15).
- Patients randomized to placebo will be administered a placebo tablet QD starting at Week 0 (Visit 2) through Week 24 (the morning of Visit 11). At Week 24, patients will be administered baricitinib 4 mg QD (or 2 mg baricitinib QD if eGFR <60 mL/min/1.73 m²)

through Week 52 (Visit 15). Patients will be eligible for rescue treatment beginning at Week 16 (Visit 9). Details of the rescue are listed in Section 5.3.3.

Patients will remain on background MTX, nonsteroidal anti-inflammatory drugs (NSAIDs), analgesics, and/or corticosteroids (see Protocol Section 9.8 for guidelines on adjustments to concomitant therapy). Patients will take their assigned doses of study drugs as directed. The primary efficacy endpoint will be at Week 12, and the final visit during Part A will be at Week 24. The final visit during Part B will be at Week 52 (Visit 15). The structural joint damage endpoints will be obtained at Weeks 16, 24, and 52. All patients who complete the Week 52 study visit will be eligible for inclusion in the extension Study JADY.

5.1.3. Part C: Post-Treatment Follow-Up Period

Patients who are not enrolled in the extension Study JADY will have a Follow-Up Visit (Visit 801) approximately 28 days after the last dose of study drug.

Patients who discontinue from the study prior to Week 52 for any reason will have an Early Termination Visit performed, including x-rays. The Early Termination Visit should be performed as soon as logistically possible because this visit includes assessment of safety. Infrequently, patient and investigator availability may be such that the Early Termination Visit and the Follow-up Visit may occur on or about the same date. In this instance, the visits may be combined and should occur approximately 28 days after the last dose of study drug. All activities required for the Early Termination Visit should be completed according to the schedule of assessments (Protocol Attachment 1).

5.1.4. Study Extensions

Patients who complete this study through Visit 15 will be eligible to participate in Study JADY, if enrollment criteria for Study JADY are met. These patients will not participate in Part C.

5.2. Determination of Sample Size

Approximately 288 patients (144 in baricitinib, 144 in placebo) will provide:

- 99% power to detect a difference between the baricitinib and placebo treatment groups in ACR20 response rate (60% versus 35%) at Week 12 based on a 2-sided chi-square test at a significance level of 0.05.

The sample size and power estimates were obtained using nQuery® Advisor 7.0.

5.3. Method of Assignment to Treatment

Patients who meet all criteria for enrollment will be randomized in a 1:1 ratio (baricitinib:placebo) to double-blind treatment at Week 0 (Visit 2). Randomization will be stratified by country and joint erosion status (1-2 joint erosions plus seropositivity versus at least 3 joint erosions). Assignment to treatment groups will be determined by a computer-generated random sequence using the interactive web-response system (IWRS).

The IWRS will be used to assign packages of baricitinib/placebo containing double-blind study drug to each patient. Each package of clinical trial material will supply sufficient medication for the number of weeks between visits. Site personnel will confirm that they have located the

correct package by entering a confirmation number found on the packages of study drug into the IWRS before dispensing the package to the patient.

5.3.1. *Treatment Administered*

This study involves a comparison of baricitinib 4 mg administered orally QD and placebo administered orally QD. Patients will continue to take background MTX therapy during the course of the study. [Table 5-1](#) shows the treatment regimens.

Table 5-1 **Treatment Regimens**

Treatment Group	Treatments Administered during Part A (Patients Not Rescued)	Treatments Administered during Part B
Baricitinib treatment	Baricitinib 4 mg ^a oral once-daily tablet	Baricitinib 4 mg ^a oral once-daily tablet
Placebo comparator	Baricitinib placebo oral once-daily tablet	Baricitinib 4 mg ^a oral once-daily tablet

^a The dose for patients with renal impairment, defined as estimated glomerular filtration rate <60 mL/min/1.73 m², will be 2 mg once daily.

The investigator or his/her designee will be responsible for explaining the correct use of study drug(s) to the patient, verifying that instructions are followed properly, maintaining accurate records of study drug dispensing and collection, and returning all unused medication to Eli Lilly and Company (Lilly) or its designee at the end of the study.

Patients will be instructed to contact the investigator as soon as possible if they have a complaint or problem with the study drug so that the situation can be assessed.

5.3.2. *Selection and Timing of Doses*

Each patient will receive blinded study drug (baricitinib 4 mg or baricitinib placebo tablets orally QD) beginning on the day of Visit 2 (Week 0). Baricitinib 4-mg oral dosing will continue daily through Visit 15 (Week 52). Baricitinib placebo oral dosing will continue daily through Visit 11 (Week 24); at Visit 11 (Week 24), all patients randomized to placebo will be reassigned to baricitinib.

Oral study drug should be taken at home at approximately the same time each day, as much as possible:

- At Visit 2 (Week 0), patients will take their study drug in the clinic.

5.3.3. *Rescue Therapy*

In consideration of the disease severity, all patients in Study JAGS will be offered rescue therapy starting at Week 16 if they are determined to be nonresponders. Nonresponse at Week 16 is defined as lack of improvement of at least 20% in both tender joint counts (TJCs) and swollen joint counts (SJCcs) at both Week 14 and Week 16 compared to baseline. At Week 16, the IWRS will assign rescue treatment based on TJC and SJC values.

All patients who are non-responders (in both baricitinib and placebo arm) will receive rescue therapy at Week 16. Patients who are nonresponders and who were randomized to placebo will

be rescued with baricitinib 4 mg. To maintain study integrity through study drug blinding, patients who were originally randomized to baricitinib will continue to receive baricitinib, with appropriate ongoing assessment of response and use of concomitant medication as needed.

After Week 16, rescue therapy will be offered to patients at the discretion of the investigator based on TJC_s and SJC_s. Once a patient has been rescued, new NSAIDs, corticosteroids, and/or analgesics may be added or doses of ongoing concomitant NSAIDs, corticosteroids, and/or analgesics may be increased at the discretion of the investigator.

A patient may only be rescued once. If a patient continues to meet nonresponse criteria for 4 weeks after rescue or at any time point thereafter, that patient should be discontinued from the study.

Patients initially randomized to placebo and not rescued before Week 24 will be reassigned to receive baricitinib 4 mg at Week 24 in order to limit exposure to inactive treatment.

Nonresponders who are rescued will receive an oral tablet daily for the remainder of the study. Rescue therapy will be administered through Week 52.

6. A Priori Statistical Methods

6.1. General Considerations

This plan describes *a priori* statistical analyses for efficacy, health outcomes, and safety that will be performed.

Statistical analysis of this study will be the responsibility of Lilly.

For continuous measures, summary statistics will include the sample size, means, standard deviations (SDs), medians, minimums, 1st quartiles (Q1), 3rd quartiles (Q3), and maximums.

For categorical measures, summary statistics will include the sample size, frequency counts, and percentages.

All statistical tests of treatment effects will be performed at 2-sided significance levels of 0.05, unless otherwise stated.

All p-values will be rounded up to 3 decimal places. For example, any p-value strictly greater than 0.049 and less than or equal to 0.05 will be displayed as 0.050. This guarantees that on any printed statistical output, the unrounded p-value will always be less than or equal to the displayed p-value. A displayed p-value of 0.001 will always be understood to mean ≤ 0.001 . Likewise, any p-value displayed as 1.000 will be understood to mean > 0.999 and ≤ 1 .

Lilly will use both an effectiveness estimand (that is, the relative effect attributable to the originally randomized treatments, baricitinib and placebo, at the primary time point in all treated patients, even if patients change treatment) and an efficacy estimand (that is, the relative effect attributable to the originally randomized treatments, baricitinib and placebo, at the primary time point in all treated patients if taken as directed) to evaluate efficacy measures at the primary time point of Week 12 for Study JAGS. All primary and secondary endpoints related to improvements in symptomatic features (that is, RA signs and symptoms, physical function, and patient-reported outcomes) are assessed prior to patients having the option to receive rescue therapy. Therefore, the only practical difference between the efficacy and effectiveness estimands for these endpoints concerns assumptions about patient response after permanent discontinuation of study drug or from the study prior to the analysis time point.

For outcome measures defined by response/nonresponse categories, nonresponder imputation (NRI) is utilized with both estimands. This approach considers study discontinuation to be a negative outcome that outweighs any potential benefit gained from hypothetical continued treatment or actual treatment and therefore fits in either the efficacy or effectiveness frameworks.

For continuous outcome measures that quantify a treatment effect, Lilly utilizes modified baseline observation carried forward (mBOCF). At the time of discontinuation, some patients may have positive outcomes (or even a range of effects) and discontinue for reasons unrelated to treatment; it seems reasonable to reflect those outcomes in the expected effects attributable to the originally randomized treatments. Other patients may discontinue because they were not seeing benefit, in which case their outcomes at the time of discontinuation should reflect their level of expected efficacy (or lack thereof) attributable to the originally randomized treatments. Finally, other patients may see positive outcomes (or even a range of effects) but be unable to tolerate or continue receiving the medicine because of adverse events (AEs). Because the latter is a

negative outcome in spite of potentially positive efficacy data, these patients will be considered to have received no improvement in their symptomatic features; therefore, the patient's baseline observation is carried forward for analysis. These approaches are reasonable for use with both the efficacy and effectiveness estimands when the inference concerns the originally randomized treatments.

For Study JAGS, Lilly plans to use this described approach for evaluating the primary endpoints. Additional sensitivity analyses are planned to investigate the robustness of this approach.

Treatment comparisons of categorical efficacy variables (including proportions of patients achieving ACR20) will be made using a logistic regression analysis with country, baseline joint erosion status (1-2 joint erosions plus seropositivity versus at least 3 joint erosions), and treatment group in the model. In general, the p-value and 95% confidence interval (CI) for the odds ratio from the logistic regression model are used for primary statistical inference. When logistic regression sample size requirements (<5 responders in any category for any factor) are not met, the p-value from the Fisher exact test is produced instead of the odds ratio and 95% CI.

Treatment comparisons of continuous efficacy and health outcomes variables will be made using analysis of covariance (ANCOVA) with country, treatment group, baseline joint erosion status, and baseline value in the model. Type III sums of squares for the least-squares (LS) means will be used for the statistical comparison; the 95% CI will also be reported.

When a restricted maximum likelihood (REML)-based mixed model for repeated measures (MMRM) is used (as a sensitivity model for continuous secondary variables [see Section 6.11.2]), the model will include treatment, country, baseline joint erosion status (1-2 joint erosions plus seropositivity versus at least 3 joint erosions), visit, and treatment-by-visit-interaction as fixed categorical effects and baseline score and baseline score-by-visit-interaction as fixed continuous effects to estimate change from baseline across post-baseline visits. An unstructured covariance structure will be used to model the between- and within-patient errors. If this analysis fails to converge, other structures will be tested such as heterogeneous autoregressive [ARH(1)], heterogeneous compound symmetry (CSH), or heterogeneous Toeplitz (TOEPH). The variance-covariance structure that results in the smallest Akaike information criterion (AIC) will be used. The Kenward-Roger method will be used to estimate the denominator degrees of freedom. Type III sums of squares for the LS means will be used for the statistical comparison; the 95% CI will also be reported. Treatment group comparisons at Week 12 and all other visits will be tested.

The Fisher exact test will be used to perform treatment comparisons for AEs, discontinuations, and other categorical safety data among treatment groups. Change from baseline in continuous vital signs, physical characteristics, and other continuous safety variables, including laboratory variables, will be analyzed using an ANCOVA model with explanatory terms for treatment and the baseline value as a covariate. Type III sums of squares will be used. The significance of within-treatment group changes from baseline will be evaluated by testing whether the treatment group LS mean changes from baseline are different from zero using a t-statistic; the standard error for the LS mean change will also be displayed. Differences in LS means as compared to placebo will be displayed with the associated p-value and a 95% CI of the LS mean difference.

In addition to the LS means for each group, the within-group p-value, the standard deviation, minimum, median, and maximum will be displayed for continuous safety variables.

Data collected at early termination visits will be mapped to the next scheduled visit number for that patient.

The following is a description of the analysis groups planned for this study. Refer to Section 6.1.3 for the definitions of analysis populations used for the efficacy and safety analyses.

Analysis Groups for the Efficacy and Health Outcomes Data

Summaries of efficacy and health outcomes data for the Week 0 to Week 12 period, the Week 0 to Week 24 period with data up to rescue, and the Week 0 to Week 52 period with data up to rescue/switch will be presented according to the following treatment groups:

- Placebo: patients randomized to placebo excluding data obtained after the receipt of baricitinib 4 mg, either as rescue therapy or according to the protocol-designated switch to baricitinib 4 mg,
- Baricitinib 4 mg: patients randomized to baricitinib 4 mg excluding data obtained after the receipt of rescue therapy.

Summaries of efficacy and health outcomes data for patients who are rescued/switched will be presented according to the following treatment groups:

- Placebo (rescued): patients randomized to placebo who were rescued on or before Week 24,
- Placebo (switched, not rescued): patients switched to baricitinib from placebo at Week 24 and not rescued after the initiation of baricitinib,
- Placebo (switched, rescued): patients switched to baricitinib from placebo at Week 24 and rescued after initiation of baricitinib,
- Baricitinib (rescued): patients randomized to baricitinib who were rescued.

Analysis Groups for the Safety Data

Summaries of safety data for the Week 0 to Week 12 period and the Week 0 to Week 24 period with data up to rescue will be presented according to the following treatment groups:

- Baricitinib 4 mg: patients randomized to baricitinib excluding data obtained after the receipt of rescue therapy,
- Placebo: patients randomized to placebo using data obtained prior to the receipt of baricitinib as rescue therapy.

Summaries of safety data for the Week 0 to Week 52 period with data up to rescue/switch will be presented for baricitinib 4 mg for patients who were randomized to baricitinib excluding data obtained after receipt of rescue therapy.

Summaries of safety data for the Week 0 to Week 52 period (including data after rescue/switch), considering all baricitinib exposures, will be presented according to the following groups:

- Placebo (rescued): patients randomized to placebo who were rescued on or before Week 24 (using data collected after initiation of baricitinib),
- Placebo (switched, not rescued): patients switched to baricitinib from placebo at Week 24 and not rescued after initiation of baricitinib (using data collected after initiation of baricitinib),
- Placebo (switched, rescued): patients switched to baricitinib from placebo at Week 24 and rescued after initiation of baricitinib (using data collected after initiation of baricitinib),
- Baricitinib (rescued): patients randomized to baricitinib who were rescued (using data collected after initiation of baricitinib),
- All baricitinib exposures across all periods, regardless of initial treatment, use of rescue treatment, or protocol-defined switch of assigned treatment, ie, pooled across all cohorts who received baricitinib (using data collected after initiation of baricitinib).

Patients who have impaired renal function who are randomized to baricitinib 4 mg will be given a 2 mg dose but analyzed in the baricitinib 4 mg group. Additional analyses for selected efficacy and safety endpoints will use this subgroup of patients (see Section 6.14 [Safety Analyses] and Section 6.15 [Subgroup Analyses]).

Summaries of efficacy and safety data collected during the post-treatment follow-up period (Part C) will be presented separately from the summaries for Parts A and B and according to the following cohorts:

- Placebo (not rescued): patients randomized to placebo who discontinued on or before Week 24 and had never been rescued at the time of discontinuation,
- Placebo (rescued): patients randomized to placebo who were rescued on or before Week 24,
- Placebo (switched, not rescued): patients switched to baricitinib from placebo and not rescued after initiation of baricitinib,
- Placebo (switched, rescued): patients switched to baricitinib from placebo and rescued after initiation of baricitinib,
- Baricitinib (not rescued): patients randomized to baricitinib who were never rescued,
- Baricitinib (rescued): patients randomized to baricitinib who were rescued,
- All baricitinib exposures across all periods, regardless of initial treatment, use of rescue treatment, or protocol-defined switch of assigned treatment, ie, pooled across all cohorts who received baricitinib prior to entering Part C.

6.1.1. *Definition of Baseline and Postbaseline Measures*

The baseline period is defined as Visit 1 through pre-dose (expected at Visit 2). The treatment period for the blinded placebo and active study drug period (Part A) starts after the first study drug administration at Visit 2 (Week 0) and ends on the date of Visit 11 (Week 24) or an early discontinuation visit before Visit 11 (Week 24). The treatment period for the unblinded active study drug period (Part B) starts after the first study drug administration at Visit 11 (Week 24) and ends on the date of Visit 15 (Week 52) or an early discontinuation visit in the treatment

period. The post-treatment follow-up period (Part C) starts after the date of Visit 15 (Week 52) or an early discontinuation visit and lasts until the follow-up visit, which occurs approximately 28 days following the last dose of the study drug, for patients who do not enter long-term extension Study JADY.

The baseline value for the efficacy analyses of the treatment period, including post-rescue analyses, is defined as the last non-missing measurement on or prior to the date of first study drug administration (expected at Week 0, Visit 2), regardless of rescue status. If the Physician's Global Assessment of Disease Activity score is recorded ≤ 5 days after the date of first study drug administration, it will still be used as the baseline value. Postbaseline measurements are collected after study drug administration (expected at Week 0, Visit 2) through Week 52 (Visit 15) or early discontinuation visit.

For data collected in the ePRO tablet related to efficacy assessments, unscheduled postbaseline visits that fall within the visit windows defined by Lilly will be summarized in the by-visit analyses if there is no scheduled visit available. That is, a +4-day window is applied to Visit 3 (Week 1) and Visit 4 (Week 2), and a +7-day window is applied to Visits 5 through 15 (Weeks 4 through 52) within the same treatment period (and while receiving the same treatment). For example, data should not be pulled across study periods for placebo group, and data cannot be pulled from postrescue visits to previous nonrescued visits. If there is more than 1 unscheduled visit within the defined visit window and no scheduled visit available, the unscheduled visit closest to the scheduled visit date will be used.

The baseline value for the safety analysis of the treatment period until rescue, protocol-defined switch, or end of study (if patients are not rescued to baricitinib 4 mg) is defined as the last non-missing measurement on or prior to the date of first study drug administration (expected at Week 0, Visit 2). The baseline value for the safety postrescue/switch period for patients randomized to placebo who are rescued/switched is defined as the last non-missing measurement obtained prior to initiation of the new treatment (baricitinib). The baseline value for the safety analyses of the postrescue period for patients randomized to baricitinib 4 mg who are rescued is the same as their treatment-period baseline. Postbaseline measurements for rescued/switched patients are collected after the rescue/switch visit through Week 52 (Visit 15) or an early discontinuation visit.

The baseline value for the efficacy analysis of the post-treatment follow-up period is defined as the last non-missing assessment at the time of Week 52 (Visit 15) or early discontinuation visit.

The baseline value for the safety analysis of the post-treatment follow-up period is defined as the last non-missing assessment on or prior to Week 52 (Visit 15) or early discontinuation visit.

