6.11.2. Secondary Efficacy Analyses

Unless otherwise stated, the following analyses will be performed to test for superiority of baricitinib relative to the placebo group.

The secondary efficacy measures are:

- Change from baseline to Week 12 in HAQ-DI score
- Change from baseline to Week 12 in DAS28-hsCRP
- Proportion of patients achieving an SDAI score ≤ 3.3 at Week 12
- Mean duration of morning joint stiffness (paper diary; 7 days prior to Week 12)
- Mean severity of morning joint stiffness (paper diary; 7 days prior to Week 12)
- Mean “Worst Tiredness” NRS (paper diary; 7 days prior to Week 12)
- Mean “Worst Joint Pain” NRS (paper diary; 7 days prior to Week 12)

The secondary efficacy measures will be analyzed using the mITT population. The PP population results will be used as supportive to the mITT results. These analyses are described as follows:

- **Comparison between baricitinib and placebo in change from baseline to Week 12 in HAQ-DI score and in DAS28-hsCRP:** an ANCOVA model with baseline score, country/region, joint erosion status, and treatment group in the model will be used to test the treatment difference between baricitinib and placebo in change from baseline to Week 12 in HAQ-DI and in DAS28-hsCRP. Type III sums of squares for the LS means will be used for the statistical comparison; 95% CI will also be reported. The LS mean difference, SE, CI, and p-value will be presented. The mBOCF approach described in Section 6.3.1 will be used to impute missing data.
- **Comparison between baricitinib and placebo in proportion of patients achieving an SDAI score ≤ 3.3 at Week 12:** A logistic regression model with treatment, country/region, and joint erosion status in the model will be used to test the treatment difference between baricitinib and placebo in the proportion of patients achieving an SDAI score ≤ 3.3 at Week 12. The NRI method as described in Section 6.3.1 will be used to impute missing data. The p-value and 95% CI of odds ratio from the logistic regression model will be reported for statistical inference. The 95% CI of responder rate difference will be calculated using the Newcombe-Wilson method (Newcombe 1998) without continuity correction.

- **Comparison between baricitinib and placebo in mean duration of morning joint stiffness in the 7 days prior to Week 12:** refer to Section 6.13 for the statistical methods used for the analysis of mean duration of morning joint stiffness.

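### Seven secondary superiority tests each use two-sided 0.05 with no order, adjustment or gate on ACR20, so family-wise error across them is not controlled

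*SAP*

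**What the plan says.** The significance level comes from one sentence in SAP 6.1, repeated in Protocol 12.2.1: "All statistical tests of treatment effects will be performed at 2-sided significance levels of 0.05, unless otherwise stated".

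SAP 6.11.2 opens its list of secondary measures with: "Unless otherwise stated, the following analyses will be performed to test for superiority of baricitinib relative to the placebo group". The seven measures are:

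1. "Change from baseline to Week 12 in HAQ-DI score" (ANCOVA)
2. "Change from baseline to Week 12 in DAS28-hsCRP" (ANCOVA)
3. "Proportion of patients achieving an SDAI score ≤ 3.3 at Week 12" (logistic regression)
4. Diary duration of morning joint stiffness (Wilcoxon rank-sum with Hodges-Lehmann estimate, SAP 6.13.1.2)
5. Diary severity of morning joint stiffness (ANCOVA)
6. Diary Worst Tiredness (ANCOVA)
7. Diary Worst Joint Pain (ANCOVA)

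The same seven are the secondary objectives in Protocol 6.2 and SAP 4.2. Protocol 12.2.7 numbers them 1 to 7 but does not call this a testing sequence; the SAP uses bullets. The SAP contents list has no multiplicity section.

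The only departures from 0.05 that I found are the interaction tests at 0.1 (SAP 6.11.1 and 6.15). The exploratory label is applied to subgroups (Protocol 12.2.10) and to the objectives and analyses in Protocol 6.3, SAP 4.3 and SAP 6.16. It is not applied to the seven.

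**The concern.** The plan has three tiers: one primary endpoint, seven secondary superiority tests and a long exploratory list. The middle tier is neither protected nor disclaimed. Each of its tests has its own full 0.05, and no rule limits the chance of an error somewhere among the seven or ties them to the ACR20 result.

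At stake is how a significant secondary result in this Phase 3 trial may be read. If, say, two of the seven reach p≤0.05, the plan gives no basis for saying whether they are confirmatory findings or what several unadjusted looks would produce by chance.

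**Working it through.** **Inputs from the documents.** Seven tests (SAP 6.11.2); two-sided 0.05 each (SAP 6.1); 144 patients per arm, ACR20 60% versus 35%, stated power 99% (SAP 5.2, Protocol 12.1); no interim analysis (SAP 6.17).

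**Assumed.** The correlation among the seven test statistics is not given. I use a common correlation ρ from 0 to 0.9, and treat each test as having exact size 0.05.

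**Step 1. The plan's own figure.** Pooled chi-square:
- Mean rate = (0.60 + 0.35)/2 = 0.475.
- SE under the null = √(2 × 0.475 × 0.525/144) = 0.0589.
- SE under the alternative = √((0.60 × 0.40 + 0.35 × 0.65)/144) = 0.0570.
- Power = Φ((0.25 − 1.96 × 0.0589)/0.0570) = Φ(2.36) = 0.991.

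The stated 99% is reproduced. The documents state no family-wise error for the secondaries.

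**Step 2. Independent tests, all seven nulls true.**
- Either direction: 1 − 0.95⁷ = 0.302.
- Favouring baricitinib only: 1 − 0.975⁷ = 0.162.
- Bonferroni upper bound, any correlation, either direction: 7 × 0.05 = 0.35.

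**Step 3. Correlated tests.** Write Zⱼ = √ρ·U + √(1−ρ)·eⱼ with independent standard normal U and eⱼ. For k true nulls and c = 1.960,

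FWER = 1 − ∫ φ(u) [Φ((c − √ρ·u)/√(1−ρ)) − Φ((−c − √ρ·u)/√(1−ρ))]ᵏ du.

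For errors favouring baricitinib only, drop the second Φ term.

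| True nulls, direction counted | ρ=0 | 0.3 | 0.5 | 0.7 | 0.8 | 0.9 |
|---|---|---|---|---|---|---|
| Seven, either | 30.2% | 27.1% | 23.0% | 17.8% | 14.9% | 11.4% |
| Seven, favouring baricitinib | 16.2% | 13.7% | 11.5% | 8.9% | 7.4% | 5.7% |
| Three, either | 14.3% | 13.6% | 12.5% | 10.9% | 9.8% | 8.4% |

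For a single test the figures are 5% (either direction) and 2.5% (favouring baricitinib).

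**Step 4. With an adjustment.** Holm's first threshold is 0.05/7 = 0.00714 (z = 2.690). With all seven nulls true, the either-direction error becomes 4.9%, 4.6%, 4.0% and 3.2% at ρ = 0, 0.3, 0.5 and 0.7.

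**Step 5. Power at that first step.** Φ(1.960 + z_power − 2.690):
- 99% at 0.05: Φ(1.960 + 2.326 − 2.690) = Φ(1.596) = 94%.
- 90% at 0.05: Φ(1.960 + 1.282 − 2.690) = Φ(0.552) = 71%.

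If tests are rejected in turn, later thresholds are 0.0083, 0.0100, 0.0125, 0.0167, 0.0250 and 0.0500.

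**The case against.** **All seven nulls being true is a worst case.** This stands. HAQ-DI and hsCRP are ACR20 components, and DAS28-hsCRP is built from joint counts, hsCRP and patient global assessment. If ACR20 really is 60% versus 35%, seven true nulls together are implausible. The three-null row is then more relevant, and it is still about two to three times 5%.

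**The two-sided figure overstates false superiority.** This also stands. A significant result favouring placebo is not a superiority finding. The directional row is about half the size and is judged against 2.5%.

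**A reader might infer that the plan allows a claim from any secondary p≤0.05 even if ACR20 fails.** The documents do not say that. They contain no claim or success rule for the secondaries. Determining superiority is the wording of the primary objective; the secondary objectives are to evaluate efficacy. SAP 6.11.2 does say these analyses test superiority, so the plan is silent on claims rather than permissive.

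**A reader might also infer that everything except the subgroup analyses is treated as confirmatory.** It is not: Protocol 6.3, SAP 4.3 and SAP 6.16 label a long list exploratory. That narrows the gap to the seven secondaries, and shows that the label was available and not used for them.

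**ACR20 is so well powered that gating changes little.** A gate alone would indeed not be enough. If the assumed ACR20 effect is real the gate opens about 99% of the time, and the seven then stand unadjusted. That is the reason for also adjusting among them.

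**Conclusion.** The gap is real: across the seven secondary superiority tests, family-wise error is uncontrolled as written. With all seven nulls true, the chance of at least one two-sided p≤0.05 is 30% under independence and 15% at a correlation of 0.8. For false superiority of baricitinib it is about 16% to 7% over the same range. With three true nulls, the two-sided chance is about 14% to 10%. These sizes depend on the number of true nulls and on assumed correlations; that they exceed the single-test level does not, so long as at least two nulls are true and their tests are not perfectly correlated.

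The ACR20 conclusion is not touched. It rests on one test with no interim look, so its type I error is as stated.

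**What to change.** Before the final database lock, after which the single unblinding takes place (SAP 7), add to SAP 6.11.2:

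*The seven secondary endpoints will be tested for confirmatory superiority only if the ACR20 comparison at Week 12 is significant at two-sided 0.05. They will then be tested by Holm's procedure across the seven at an overall two-sided 0.05. All other efficacy p-values are nominal.*

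Protocol 12.2.1 lets analysis changes that do not alter a principal feature be made in the SAP and clinical study report, with justification, so a protocol amendment may not be needed.

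No data collection or sample size changes. The cost is some power. The smallest of the seven p-values must be ≤0.0071; at that step, 99% power at 0.05 becomes about 94% and 90% becomes about 71%. That threshold binds only the smallest p-value, and later steps relax up to 0.05. The documents give no power for any secondary endpoint, so the loss for a particular one, such as SDAI remission, cannot be stated.

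If the sponsor intends no confirmatory secondary conclusions, one sentence in SAP 6.11.2 stating that the secondary p-values are nominal closes the gap instead and costs no power.
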